Intravenous Radiocontrast Agent Omnipaque 350 and Oral Beta Blocker: Most people do not experience side effects or complications; however, out of more than 73,000 patient studied²⁵, Mild to moderate reactions - defined as reactions that either require no therapy or if therapy is given and patient is sent home from the radiology department - occur in 0.2% of cases. Severe reactions that necessitate intravascular epinephrine use in the emergency room or urgent therapy and follow up in the ER or hospital admission occur in 0.016% of cases. The risk of death is 1/100,000 patients²⁵. Potential side effects of non-ionic iodinated contrast that can cause adverse reactions include: Death (1/100,000 persons), sneezing and nasal congestion, hives, itching, rash, and swelling; laryngeal (oral) edema; bronchospasm; and anaphylaxis, rigors (shaking, chills, fever); seizure; numbness; malaise and achiness; pulmonary edema; chest pain; and hypertension²⁵.

The radiocontrast agent given along with saline intravenously during cardiac CT will be Omnipaque 350 iodinated contrast unless the decision is made by radiology staff to substitute a different FDA-approved iodinated contrast agent.

A Beta blocker, Metoprolol, is often given before undergoing CT scans. The patient's clinical staff providing care and/or the radiologist at the diagnostic imaging department at the time of the scan will determine whether administration of a beta blocker is necessary before CT scan and will not be administered to a patient if a contraindication exists.

Needle Insertion

Insertion of the needle to administer contrast may cause minor pain, bruising and/or infection at the injection site.

Risk Minimization

All efforts will be made to keep confidentiality. Safeguards will be in place to protect the identity of the patients and their private health information. Study ID will be assigned by the study coordinator, and all following collected data will be connected with this study ID, but not with the name of the patient. Private health information connected with patient's name will be locked in a secure location in the office, and limited number of people will have access to it (PI and study coordinator).

IVs and or blood draws will be performed by trained research coordinators using good clinical practice and standard aseptic technique.

Gadolinium administration:

Patients with renal insufficiency with GFR <30ml/min and pregnant women will be excluded to minimize any risks associated with gadolinium administration for the contrast-enhanced MRI. A physician will be available during the procedure to administer any necessary care if side effects do occur, and to determine when or if the injection of the gadolinium should be stopped.

MRI examination:

No one will be allowed to enter the magnet room when a patient is in the magnet room unless they are involved in the study. No one will be allowed to bring magnetic metal objects near the magnet when other persons are in or near the magnet. The magnet room will be kept closed during the study, and will be opened only by the technologist at the end of the study. Individuals with metal implants and fillings are excluded from the study as described in the exclusion criteria. Patients will be asked to leave magnetic metal objects outside the magnet room, and patients will be required to fill out a questionnaire regarding MR safety and the presence of metal objects in their bodies. Care will be taken to limit the RF power deposition and gradient rise times to well within FDA guidelines. The MRI scanner's software contains safeguards to prevent both excessive RF power and above-threshold gradient changes. The operating technologist will be in voice contact with the patient, and the patient will be told that he/she can contact the operator at any time with a request to be taken out of the magnet. All subjects will be carefully screened for the presence of any contraindications prior to them signing the consent form.

Six Minute Walk Test:

CPR certified personnel will accompany the participant and access to emergency equipment will be available. The participants' vital signs will be monitored before and after the six minute test.

Psychological risk:

The psychological risk of participating in the study may be a transient increase in worry about potential disease. Subjects will be given the opportunity to ask questions of study personnel on this topic. The study coordinators and investigators have extensive experience working with patients with these diseases.

Pregnant women:

Most women included in this study will not be of child-bearing potential (post-menopausal). Women of child-bearing potential who are not on reliable birth control (as assessed by physician) will have a urine HCG test done to obtain pregnancy status before MRI is performed. MRI with contrast will not be performed on a pregnant woman. If participants become pregnant over the course of the study, they will be asked to notify their physician immediately. If patients who become pregnant have already completed the cardiac MRI, they will be maintained as study participants, otherwise they will be excluded. There is no additional risk of CRT to pregnant women.

cCT examination:

Cardiac CT will be acquired using a prospective scan. Total effective dose is 3-4mSv, the equivalent of 7.5-10 mammograms.²⁶ Patients will complete both the "Cardiac CT Screening Form" and "Patient Contrast Questionnaire and Procedure Record" prior to undergoing scanning. These two forms are standard procedure in the OHSU diagnostic radiology department prior to CT scanning with contrast. The OHSU diagnostic radiology department will review both forms before scanning.

IVs and or Blood Draws

All IVs and/or Blood Draws will be performed by trained research coordinators or clinical staff using standard OHSU clinical practice and standard aseptic technique.

CT Contrast administration - GFR:

Patients with renal insufficiency with GFR <30ml/min and pregnant women will be excluded to minimize any risks associated with contrast administration for the contrast-enhanced CT. A physician will be available during the procedure to administer any necessary care if side effects do occur, and to determine when or if the injection of the contrast should be stopped.

A GFR test will be ordered and paid for by the study team in the event of any of the qualifying criteria below exist in an enrolled subject. The patient will complete the test according to the following timeline per criteria based off Policy # 300.02 in the OHSU Diagnostic Radiology manual.

1)Creatinine/eGFR required within 30 days of CT scan:

Patients >60 years of age

Patients with a history of hypertension requiring medication

Patients with diabetes mellitus

Patients with kidney disease: kidney transplant, single kidney, kidney cancer, kidney surgery

2) Creatinine/eGFR required within 24 hours of CT scan:

Patients whose most recent eGFR<60 and >30

Any patient whose most recent eGFR <30 will be excluded from the study

Plan for reporting unanticipated problems or study deviations.

Data Safety Monitoring Board is monitoring safety of participants and study conduct.

Serious adverse advents will be reported to the IRB

Potential Benefits

There is potential for benefit to the patient since this is the patients' last opportunity to get quality imaging of their heart before CRT implantation. All patients are about to receive a CRT device. CRT devices create immense amounts of artifact on both MRI and CT. Images will be made available to the patients' treating physicians.

This study will advance our understanding of the mechanisms of reverse electrical and mechanical remodeling with aCRT, and will help in identifying appropriate candidates for aCRT.

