Study protocol will be reviewed and approved by the OHSU IRB before the beginning of the enrollment in the study. All study participants will sign consent form before entering the study. We will request IRB to give us permission (via a Prep to Research form) to review medical records of study candidates for inclusion/exclusion criteria. This information will not be recorded. The research study coordinator will screen the OHSU Arrhythmia and Heart Rhythm Clinic schedule through Epic for patients who may be candidates for CRT and will contact the care provider to discuss if patient is a candidate. Patients, who have approved class I-II indications for CRT-D or CRT-P according to current guidelines, who are scheduled for Medtronic CRT-D or CRT-P device implantation will be approached in the clinic at the time of scheduling for CRT implantation. At this point the study and informed consent form will be explained to the patients. These patients who are willing and able to sign the consent form will be invited to participate in the study and a baseline enrollment visit will be scheduled. Final determination of eligibility will be made during the initial visit and scheduled baseline study visit. After signing consent form eligible study candidate will become study participant.

Randomization

Assignment of patients into aCRT on or off will occur through the randomization module in REDCap. Only the study coordinator and primary investigator will have access to view patient treatment assignments on the REDCap database. The following information outlines the randomization module implemented via REDCap.

The unit of randomization: a person (study participant).

The type of randomization: random stratified block

Assignment ratio: 1:1

Assignment strata: (1) gender (male vs female); (2) cardiomyopathy type (ischemic vs. non-ischemic).

Block size: random (2, 4, or 6) with allocation proportional to the elements of Pascal's triangle.

Random seed used and the randomization list were created using the –ralloc- program in Stata version 13.1

Randomization will be enacted via an envelope-based system, via sealed envelopes containing randomization assignments. Random treatment assignments will be placed in advance in a set of sealed envelopes. Each envelope will be numbered (#1-32),

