with 12-leads and orthogonal ECG during bi-ventricular pacing ON (5 min) and OFF (during 10 min). CRT-D device will be interrogated, and all events with stored EGMs will be then translated with translational utility and further analyzed. Echocardiogram will be performed and fully analyzed to assess mechanical response to CRT after 6 months of CRT.

After that, at 12-month post CRT, and then during 5 years once a year – phone call F/U (collection of the history of hospitalizations, ICD shocks, death), RedCap surveys, remote device follow-up

Study Exit/Withdrawal

Terms under which subjects can/will be exited

- Subject death
- Subject lost to follow-up
- Subject no longer able to perform study follow-up procedures, or unwilling to continue follow-up and withdraw study consent.
- Subject becomes pregnant before cardiac MRI procedure.

Statistical Methods and Data Analysis

Primary Outcome: There are **2 primary outcomes** in this study: (1) regression slope of Electrical Dyssynchrony Index values measured by ECGi 6 months post-CRT, regressed against Electrical Dyssynchrony Index values measured by ECGi prior CRT; Only randomized patients (treatment arm adaptive CRT, and control arm regular CRT) will be included in this analysis. (2) difference in regression slopes of SAI QRST against Electrical Dyssynchrony Index values measured by ECGi vs. QRS duration against Electrical Dyssynchrony Index (EDI) values measured by ECGi. All study participants (randomized two arms, and non-randomized registry arm) will be included in this analysis.

Main analysis: linear regression

Predictors:

Electrical Dyssynchrony Index The electrical dyssynchrony index (EDI) is computed as the standard deviation of activation times at 350/700 sites on the LV epicardium.

SAI QRST

QRS duration

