The proposed predictors as variables of interest will be measured as continuous variables and could be dichotomized or divided by quartiles. The distribution of variables of interest will be defined, and Log transformation (or other transformation, if required, depending on the particular case) will be performed for any variable that displays non-normal distribution, with subsequent verification of an achieved normal distribution. Simple and multiple linear regression models will be explored to determine factors that may play the role of predictors of our tested marker of interest, presented as a normally distributed continuous variable. For such linear regression models, the tested marker will be an outcome variable.

Results will be presented as mean \pm standard deviation (SD) for normally distributed variables, and as median and inter-quartile range for non-normally distributed variables. Continuous variables will be compared using the independent samples *t* test if normally distributed and the Wilcoxon rank sum test if skewed. The Pearson chi-square test will be used to compare categorical variables. A *p*-value of <0.05 will be considered significant.

Justification for Sample Size

We are planning a study with 15 experimental subjects and 15 controls in which we will regress values of Electrical Dyssynchrony Index values measured by ECGi 6 months post-CRT against Electrical Dyssynchrony Index values measured by ECGi prior CRT within each treatment group. Prior data¹⁷ (Ghosh et al, 2911) indicate that the standard deviation of Electrical Dyssynchrony Index is 3.9 and 2.3 in the responders and non-responders, respectively. We conservatively assumed that the standard deviation of the Version 6 Electrical dyssynchrony measures: Adaptive CRT effect (ELDYSME aCRT)

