regression errors will be 0.08. If the true difference in the slopes of these 2 regression lines is 0.05, we will be able to reject the null hypothesis that these slopes are equal with probability (power) 0.954. The Type I error probability associated with this test of this null hypothesis is 0.05. Figure 1 below illustrates the difference in statistical power as a function of sample size and the difference in regression slopes ($\lambda_2 - \lambda_1$) that we wish to detect. Therefore, estimated sample size is 30 study participants (15 in experimental aCRT arm, and 15 in control arm). After adjustment of the sample size for a loss of follow-up (+ 6%) estimated sample size is 32 participants (16 in experimental aCRT arm, and 15 in control arm).

[figure not shown]

Figure 1. Statistical power estimation as a function of sample size of aCRT arm for a range of the differences in the slopes of the regression lines for the experimental and control groups that we wish to detect (shown by different colors).

Risk Analysis

Potential Risks

This is a randomized clinical trial of 2 FDA-approved CRT strategies. Patients will receive commercially available FDA-approved device. There is no incremental risk of health for study participants.

Very low risk of confidentiality loss always exists in any clinical research. All efforts will be made to keep confidentiality. Patient will be notified immediately if any unforeseen breach in confidentiality occurs (e.g. stolen computer). Safeguards will be in place to protect the identity of the patients and their private health information. Study ID will be assigned by the study coordinator, and all following collected data will be connected with this study ID, but not with the name of the patient. Private health information connected with patient's name will be locked in a secure location in the office, and limited number of people will have access to it (PI and study coordinator).

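### The primary EDI regression leaves out both randomisation strata; if they predict 6-month EDI, it is less efficient than an adjusted model

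*Combined protocol and SAP*

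**What the plan says.** The Randomization section describes stratified blocks of random size 2, 4 or 6, allocated 1:1: "Assignment strata: (1) gender (male vs female); (2) cardiomyopathy type (ischemic vs. non-ischemic".

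Statistical Methods and Data Analysis defines primary outcome 1 as the slope of 6-month EDI on pre-implant EDI in the randomised patients. It gives "Main analysis: linear regression" and lists EDI, SAI QRST and QRS duration as predictors. Justification for Sample Size repeats the model: "we will regress values of Electrical Dyssynchrony Index values measured by ECGi 6 months post-CRT against Electrical Dyssynchrony Index values" before CRT, separately in each arm. Neither stratum is mentioned in these sections. Multiple regression appears only as an exploration to find predictors, with no covariates named.

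The power statement belongs to the same regression. The error SD is assumed ("regression errors will be 0.08"), the effect is given as "If the true difference in the slopes of these 2 regression lines is 0.05", and the result is "we will be able to reject the null hypothesis that these slopes are equal with probability (power) 0.954".

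The Primary Objectives describe the same question differently: whether aCRT reduces EDI more than standard CRT, measured as change in EDI from baseline to 6 months. That points to an arm effect as well as a slope contrast.

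**The concern.** Blocking within strata makes the arms alike on gender and cardiomyopathy type. If those factors predict 6-month EDI and the model omits them, their contribution stays in the residual variance. Two consequences are possible.

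- **Slope contrast.** The test works with more noise than it needs to and forgoes power.
- **Baseline-adjusted arm effect.** The estimate already benefits from the balance, but the model's standard error does not reflect it. The standard error is too large and the test is conservative.

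There is also a prespecification point. Because covariates enter only through exploration, the strata could be added or left out after the results are seen. With 15 evaluable patients per arm, neither wasted precision nor an open modelling choice is welcome.

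**Working it through.** **1. Reproduce the stated power.** Inputs from Justification for Sample Size: 15 per arm, slope difference 0.05, error SD 0.08, alpha 0.05 (two-sided assumed). The spread of baseline EDI is taken as 2.3 in both arms, the smaller of the two SDs quoted there.

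- SE = 0.08 × √(2 / (14 × 2.3²)) = 0.08 × 0.1643 = 0.01315
- 0.05 / SE = 3.803; t(0.975, 26 df) = 2.056
- Power = P(T₂₆ < 3.803 − 2.056) = 0.9538

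This matches 0.954. The calculation contains no stratum terms, so 0.08 is the error SD of the unadjusted model.

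**2. Add the strata on the same inputs.** Let R² be the share of residual variance that the strata explain. It is not in the documents; 0 to 0.3 is assumed. The error SD becomes 0.08 × √(1 − R²) with 24 df.

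This form counts only the lost degrees of freedom. The strata will also correlate by chance with the arm-by-baseline term. That term has 30 − 3 = 27 dimensions once intercept, arm and baseline are fitted, and two more columns take about 2/27 of its information. The last column therefore multiplies the signal-to-noise ratio by √(25/27) = 0.962.

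| R² | Error SD | Power, df only | Power, with chance correlation |
|---|---|---|---|
| 0 | 0.0800 | 0.953 | 0.938 |
| 0.1 | 0.0759 | 0.968 | 0.957 |
| 0.2 | 0.0716 | 0.981 | 0.973 |
| 0.3 | 0.0669 | 0.990 | 0.985 |

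On the plan's own inputs, adjustment changes power by −0.1 to +3.6 points on the first count, and by about −1.6 to +3.1 points on the second.

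**3. Away from the ceiling.** Simulation: 30 patients, blocks of 2/4/6 within the four strata, an assumed 30% women and 50% ischemic, and an alternative chosen to give slope-test power near 0.75.

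| R² | Slope power, no strata | Slope power, with strata | Arm-effect type I error, no strata |
|---|---|---|---|
| 0.1 | 0.755 | 0.757 | 0.042 |
| 0.2 | 0.742 | 0.796 | 0.038 |
| 0.3 | 0.741 | 0.852 | 0.025 |

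- The slope test gains about 0, 5 and 11 points. Other runs of the same design gave 8 or 9 points at R² = 0.3.
- Adding the strata restores the arm-effect type I error to about 0.05. Arm-effect power rises from 0.67–0.69 to 0.70–0.71, 0.74–0.77 and 0.77–0.81.
- If the strata explain nothing, the slope test loses 3 to 4 points and the arm effect about 1 point or less.
- Without strata, the slope test's own type I error was 0.049, 0.052, 0.051 and 0.047 at R² = 0, 0.1, 0.2 and 0.3, which is nominal.

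**4. Check on the conservatism.** With perfect balance on the strata, the true standard error of the arm effect is √(1 − R²) times the reported one. The type I error is then P(|T₂₇| > 2.052 / √(1 − R²)). The cut-offs are 2.163, 2.294 and 2.452, giving 0.040, 0.030 and 0.021. The simulated values lie slightly higher, as expected when 30 patients in four strata leave some blocks incomplete.

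**The case against.** A reader might infer that omitting the strata makes the error variance larger than the design allows, so that the trial falls short of its stated power. The documents do not support that. The 0.08 is assumed for the regression without strata, and 0.954 reproduces without them. Only if 0.08 were a stratum-adjusted SD would omission lower the planned power (to 0.934 at R² = 0.1 and 0.865 at R² = 0.3), and nothing says that it is.

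A reader might also infer that the specified test is invalid. It is not. Stratified blocks balance the arms on the strata, which does not distort the standard error of a slope difference. The conservatism belongs to the arm effect alone, and it produces no excess of false positives.

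The strongest remaining objection is that the benefit is hypothetical. No association between either factor and EDI is documented, the proportions of women and ischemic patients are assumed, and the slope test gains almost nothing at R² = 0.1 and loses a little at zero. With 30 patients, an unadjusted slope test is defensible. That stands, and it limits the weight of the point. It does not justify leaving the choice unstated.

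It is also fair to say that the section has a larger problem. An error SD of 0.08 beside EDI SDs of 2.3 and 3.9 implies that baseline EDI explains 1 − 0.08²/2.3² = 99.88% to 1 − 0.08²/3.9² = 99.96% of 6-month variance, if the SD at 6 months is similar. With an error SD of 1, power is about 0.059, and adjustment at R² = 0.3 moves it only to 0.063. Adding the strata would not repair that.

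**Conclusion.** The point holds as a modest matter of efficiency and prespecification. The stratification factors are absent from the primary outcome 1 model, and the only route by which they could enter is exploratory. The stated 0.954 is unaffected and the slope-difference test is valid.

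Any loss is relative to an adjusted model: roughly 0 to 11 points of slope-test power at a base near 0.75, and an arm-effect test run at about 0.04 to 0.025 instead of 0.05. Both ranges assume that the strata explain 10% to 30% of residual EDI variance, with 30% women and 50% ischemic patients; none of these figures is in the documents. If the strata are unrelated to EDI, adjustment costs a little power and gains none.

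**What to change.** In Statistical Methods and Data Analysis, beside the main-analysis statement, specify the model for primary outcome 1: 6-month EDI on arm, baseline EDI, gender and cardiomyopathy type, plus the arm-by-baseline term if the slope contrast is kept. State that the two strata are fixed main effects chosen in advance.

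The cost is one sentence and two degrees of freedom, with no new data, since both factors are recorded for randomisation. If neither factor is related to EDI, the price is about 1 point of power for the arm effect and 3 to 4 points for the slope test at a base near 0.75. On the plan's own inputs it is about 0.1 point from the degrees of freedom alone, or about 1.6 points once chance correlation with baseline EDI is counted. The support for the 0.08 error SD needs separate attention.

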Study will be conducted at the Oregon Health & Science University. It is a prospective, single-center, randomized, double-blind paralleled controlled clinical trial. As estimated, 32 participants will be enrolled. All study participants will get commercially available Viva™ XT CRT-D device. Participants will be randomized 1:1 to one of two pacing therapy arms, aCRT ON or aCRT OFF (traditional BiV CRT). Patients who are receiving CRT device without available adaptive CRT feature (i.e. it is impossible to program adaptive software feature ON or OFF) per their clinical team (post-screening) will be placed into a third, non-randomized, non-blinded CRT registry arm. Study participants will undergo cardiac MRI and ECGi before device implantation. A second ECGi will be performed within two weeks hours after CRT implantation. Duration of assigned intervention is 6 months. At least 6-month post CRT (within 30-day interval) participants will undergo a 3rd ECGi and echocardiogram. There are **2 primary outcomes** in this study: (1) regression slope of Electrical Dyssynchrony Index values measured by ECGi 6 months post-CRT, regressed against Electrical Dyssynchrony Index values measured by ECGi prior CRT; (2) difference in regression slopes of SAI QRST against Electrical Dyssynchrony Index values measured by ECGi vs. QRS duration against Electrical Dyssynchrony Index (EDI) values measured by ECGi.

Background and Justification

Cardiac resynchronization therapy prolongs life and decreases risk of heart failure exacerbation in patients with low ejection fraction (EF) and wide QRS.⁶⁻⁹ Aging population with high prevalence of obesity, diabetes and hypertension, along with advancements in the treatment of acute cardiovascular diseases resulted in an increase in the incidence and prevalence of the heart failure (HF) over the past decades. Studies estimate that about 2-3% of the population suffer from HF. Despite advances in therapy and management, HF carries substantial morbidity and mortality, and high rates of hospitalizations and hospital readmissions represent large burden to the health-care system. CRT is an effective treatment for patients with HF, wide QRS, and reduced EF. However, about 30% of CRT recipients do not demonstrate mechanical response on CRT.

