[figure not shown]
Methodology

Study Design

We will conduct an investigator-initiated prospective, single-center, randomized, double-blind paralleled controlled clinical trial comparing adaptive cardiac resynchronization therapy (aCRT)¹ to standard CRT in patients with currently approved (class I-II) indications for CRT². Following verification that inclusion/exclusion criteria are met, all patients will undergo baseline evaluation/testing. All study participants will receive the commercially available Medtronic Viva™ XT CRT-D Model DTBA1D4, DTBA1D1, Viva™ Quad XT CRT-D Model DTBA1Q1, DTBA1QQ, Viva™ Quad S CRT-D Model DTBB1Q1, DTBB1QQ, Viva™ S CRT-D Model DTBB1D1, DTBB1D4 or Viva™ XT CRT-P Model C6TR01. These devices are already used in standard-of-care for patients receiving CRT implantations. No co-investigators will be paid by Medtronic funding for use of these devices. Following successful implantation, ECG/EGM recording and device programming will be performed according to the protocol and participants will be randomized to either the aCRT ON or the aCRT OFF pacing arm. Should implantation or randomization not be successful, patients will be followed as defined in further sections. Protocol-required 6-month follow-up visit will occur at least 6 months post randomization (within 30-days window). Patients will remain randomized in the assigned therapy arm until 6-month follow-up visit. After that, no study visits are planned. Follow-up will continue during next 5 years remotely (via phone, remote follow-up, RedCap surveys).

Study Schema

Subject Selection

Number of patients: The study will require up to 16 patients randomized to one of two pacing therapy arms (up to 32 patients enrolled).

Patients of both genders with mild to moderate heart failure who meet all inclusion/exclusion criteria are eligible for this study. Listed below are the specific inclusion and exclusion criteria:

Inclusion criteria:

- Patient has a standard class I or class II indications for CRT-P or CRT-D implantation in accordance with ACC/AHA/HRS guidelines (2012 ACCF/AHA/HRS Focused Update Incorporated Into the ACCF/AHA/HRS 2008 Guidelines for Device-Based Therapy of Cardiac Rhythm Abnormalities)². At least 18 years of age at the time of consent
- Is willing and able to comply with the protocol

Exclusion criteria:

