opaque, and otherwise tamperproof. When a participant is randomized, **his/her name and the number of the next unopened envelope are first recorded in the presence of a second staff member and both sign the envelope**. Then the envelope is opened, and the treatment group contained therein assigned to the participant and recorded on a log.

Study participants who, because of clinical reasons per clinical team decision, will receive a CRT device without the adaptive software feature enabled will NOT be randomized, but instead, will be included in the study registry arm.

Blinding, or Masking

In order to minimize the introduction of bias, this study will be double-blinded (double-mask). Patients will not have access to their randomization assignment. To obtain non-biased information and perform non-biased assessments, physicians and their staff who will evaluate NYHA classification and heart failure stage, and administer the Minnesota Living with Heart Failure Questionnaire, and Patient Global Assessment tools will be masked to the patient's assignment and device programming. Un-masked physicians and staff will be responsible for randomization, programming the system, monitoring the system performance, and collecting system data for this study. Study personnel will be trained to take special care to ensure that patients do not inadvertently learn of their assignment as a result of communication with their care provider. A log will be maintained to identify staff that will remain blinded to the randomization assignment and programming.

Data Collection

For patients that meet all inclusion/exclusion criteria, are enrolled in the study, clinical data will be collected for patient history, implant, pre- and post-implant baseline evaluation/testing, randomization, protocol-required scheduled follow-up visit, remote follow-up visits, system modification and study exit (including death) until study closure (5 years). Hospitalizations and adverse events (including adverse event-related emergency department and urgent care visits) will be reported until the patient exits the study or study closure.

All data will be entered in the digital secure web-based database (REDCap Consortium partner <http://www.project-redcap.org/>).

Data collection requirements are summarized in Table 1.

Subject Follow-Up Schedule

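### The sample size of 32 is split 16 + 15 = 31, and the plan does not say whether non-randomised registry participants count toward the 32

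*Combined protocol and SAP*

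**What the plan says.** All references are to the combined protocol and SAP.

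- **Justification for Sample Size.** Before loss to follow-up, the "estimated sample size is 30 study participants (15 in experimental aCRT arm, and 15 in control arm". The next sentence inflates this: "After adjustment of the sample size for a loss of follow-up (+ 6%) estimated sample size is 32 participants". The split given for the inflated total is 16 and 15: "estimated sample size is 32 participants (16 in experimental aCRT arm, and 15 in control arm".
- **Randomization.** "Assignment ratio: 1:1". On the sealed envelopes: "Each envelope will be numbered (#1-32". On patients whose device lacks the adaptive feature, the section says that they "will NOT be randomized, but instead, will be included in the study registry arm".
- **Study Scope.** "As estimated, 32 participants will be enrolled". The same paragraph then introduces 1:1 randomisation and, after it, the third, non-randomised registry arm.
- **Subject Selection.** "The study will require up to 16 patients randomized to one of two pacing therapy arms (up to 32 patients enrolled".
- **Informed Consent Process.** An eligible candidate becomes a study participant on signing consent, which comes before implantation.
- **Statistical Methods and Data Analysis.** The first primary outcome is analysed in randomised patients only. The second uses all study participants, and the registry arm is expressly listed among them.

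No section gives a size for the registry arm or says whether it is additional to the 32.

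**The concern.** There are two separate faults in the number that governs when recruitment stops.

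The first is arithmetical. The two arm sizes do not add up to the total in the same sentence. The control arm is left at its size before inflation, so it carries no allowance for the 6% loss.

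The second is one of definition. The calculation needs 32 randomised patients, while two other sections state 32 enrolled. These are the same number only if everyone enrolled is randomised, and the plan provides for people who are not. Some registry entry is foreseeable: Study Purpose lists device models without the adaptive feature (Viva Quad S and Viva S) among the study devices and leaves the choice of model to the implanting physician. If registry participants took places within the 32, each would reduce the randomised comparison behind the first primary outcome. Two people running this trial could reasonably stop recruitment at different points.

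**Working it through.** **1. The plan's total.** Inputs from Justification for Sample Size: 15 evaluable per arm (30 in total) and 6% loss.

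- 30 / (1 − 0.06) = 31.9, rounded up to 32. The cruder 30 × 1.06 = 31.8 also rounds up to 32. The total reproduces.
- Per arm: 15 / 0.94 = 15.96, rounded up to 16. The consistent split is 16 + 16 = 32.

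**2. The printed split.**

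- 16 + 15 = 31, one short of 32.
- Evaluable after 6% loss: 16 × 0.94 = 15.04 in the aCRT arm, 15 × 0.94 = 14.1 in the control arm, 29.1 in total. The control arm falls below the 15 that the calculation uses.

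**3. The plan's power, then power under the printed split.** Inputs from the same section: slope difference 0.05, SD of regression errors 0.08, type I error 0.05 (taken as two-sided; the plan does not say). The plan gives two SDs for the Electrical Dyssynchrony Index, 3.9 and 2.3, and does not say which enters the calculation.

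SE = 0.08 × √[1/((n₁−1)·SD₁²) + 1/((n₂−1)·SD₂²)], with n₁ + n₂ − 4 degrees of freedom.

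- 15 and 15, SD 2.3 in both arms: SE = 0.08 × √[2/(14 × 5.29)] = 0.01315; 0.05/0.01315 = 3.80; critical t on 26 df = 2.056. Power is 0.954 by the shifted t and 0.955 by the noncentral t. This reproduces the stated 0.954, so SD 2.3 in both arms is used below.
- 15 and 14 on the same basis: SE = 0.0134; ratio 3.73; critical t on 25 df = 2.060. Power is 0.947 to 0.948.
- With SDs of 3.9 and 2.3, power at 15 and 15 is 0.992 to 0.994. That does not match the stated figure, and it makes every scenario below look better.

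**4. If registry participants used places within the 32.** The number in the registry, r, is an assumption, since the documents give none. Expected evaluable per arm = (32 − r) × 0.94 / 2.

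| r (assumed) | Randomised | Expected evaluable per arm |
|---|---|---|
| 0 | 32 | 15.04 |
| 1 | 31 | 14.6 |
| 3 | 29 | 13.6 |
| 6 | 26 | 12.2 |
| 10 | 22 | 10.3 |

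By the formula in step 3 with SD 2.3 in both arms, power is 0.92 at 13 per arm, 0.89 at 12 and 0.82 at 10. These are the per-arm values for r = 3, 6 and 10 rounded down to whole patients, so they slightly overstate the loss.

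**5. If the registry is additional.** Enrolment needed to randomise 32 is 32 / (1 − s), where s is the assumed share of those enrolled who go to the registry: 34 at 5%, 36 at 10%, 40 at 20%, 46 at 30%.

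**The case against.** On the split, the other side can say that 15 is a one-digit slip which the rest of the plan corrects. The total of 32 is right, the ratio is 1:1, there are 32 envelopes, and Subject Selection gives 16, which only makes sense per arm. Staff working from those sections would randomise 32, so the misprint might never take effect. This is probably so, and the loss even if it did is under one percentage point of power. It remains a wrong figure in the section that defines the sample size.

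On the registry, a reader might infer that the cap of 32 includes registry participants, so that each one necessarily shrinks the randomised comparison. The documents do not support that as a statement of fact. No section says that registry participants count toward 32. Study Scope offers 32 as an estimate, not a cap, and brings in the registry only afterwards as a third arm. Only Subject Selection says up to 32, in a parenthesis attached to the two randomised arms. The sample size is derived from those two arms alone, and 32 envelopes would be surplus if the registry consumed places. These points favour 32 randomised as the intention. They do not remove the conflict, because the word used is enrolled, and the plan makes registry patients study participants from consent onward.

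A reader might also infer that the trial is underpowered. On the plan's own inputs it is not: with SD 2.3 in both arms, power is still 0.82 at 10 per arm, and if one arm had SD 3.9 it would be about 0.93 there.

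**Conclusion.** The point holds in two parts. First, the printed split is wrong. It sums to 31, contradicts the plan's own total, ratio and envelope count, and leaves about 14 evaluable controls where 15 are required. The effect on power is small. Second, whether 32 means enrolled or randomised is unresolved, because the plan never says if the registry arm is additional. There is no slack to absorb the uncertainty: 32 randomised gives an expected 15.04 per arm, so any registry participant counted within the 32 takes the expected number below target.

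The size of the second part depends on a registry count that the documents do not give, and the power figures rest on SD 2.3 in both arms, two-sided 0.05 and the plan's error SD of 0.08, all taken as given. The finding is that the plan as worded does not secure its stated 15 per arm. It is not a finding that registry patients do consume the 32 places, nor that power is inadequate. It should be corrected because the number governs recruitment for a primary outcome in a very small trial.

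**What to change.** - In Justification for Sample Size, change the split to 16 + 16 = 32.
- In Study Scope, Subject Selection and Justification for Sample Size, state that 32 patients will be randomised, 16 per arm, and that registry participants are counted separately. Give the registry its own expected or maximum number.
- If 32 is instead meant as a total cap that includes the registry, say so, and restate the expected number randomised, the evaluable number per arm and the power.

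The first two changes are wording in three sections and leave the design as it is; total enrolment would exceed 32 by the size of the registry. The third also needs a revised power statement, which will be lower than 0.954 on the same inputs.
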